7.3.6 Adverse Events of Special Interest

irAEs are considered AEs of special interest. Participants should be evaluated carefully for potential IRRs as described in [Section 2.3.1]. In the event a participant is diagnosed with an IRR, then it should be reported as an AE using the diagnosis rather than the list of symptoms. Additional information on the AE of IRR will be collected on the AE eCRF.

If the IRRs are also classified as serious, they are to be collected via the SAE/Special Situation worksheet and reported within 24 hours as described in [Section 10.3.6 Reporting of Serious Adverse Events].

7.3.7 Special Situations

Certain special situations observed in association with the IP, such as incorrect administration (e.g., wrong dose of IP or background therapy) are reported as protocol deviations and/or may require special reporting, as described below. These special situations are not considered AEs, but do require to be communicated to Astellas as per the timelines defined below.

If a special situation is associated with, or results in, an AE, the AE is to be assessed separately from the special situation and captured as an AE on the eCRF. If the AE meets the definition of an SAE, the SAE is to be reported as described in [Section 10.3.6 Reporting Procedures for Serious Adverse Events] and the details of the associated special situation are to be included in the clinical description on the special situation worksheet or pregnancy reporting form.

The special situations are:

- Pregnancy
- Lactation
- Medication error, overdose and use outside protocol
- Misuse/abuse
- Occupational exposure
- (Suspicion of) Transmission of infectious agent
- Suspected drug-drug interaction

Instructions and procedures for reporting special situations are provided in [Section 10.3.7 Reporting Procedures for Special Situations].

7.4 Pharmacokinetics

Whole blood will be collected to monitor pharmacokinetics of ASP0739 cells via determination of genomic DNA in the cell by a quantitative polymerase chain reaction method for the dose escalation cohort, expansion cohort and safety lead-in cohort. Sampling time points are as shown in the schedule of assessments [Table 5].

Serum concentrations of pembrolizumab will be evaluated in the combination therapy arm, including safety lead-in, as outlined in the schedule of assessments [Table 5].

Refer to the laboratory manual for detailed information regarding sampling, processing, shipping and storage instructions.

7.5 Pharmacodynamics/Biomarker

Samples for exploratory pharmacodynamics and biomarker analyses of ASP0739 will be collected according to the schedules of assessments [Table 1 and Table 2].

The samples described in [Sections 7.5.1 Blood Samples, 7.5.2 Tumor Tissue Samples and 7.5.3 Buccal Swab Samples] may be analyzed for other biomarkers including DNA, RNA and protein, to investigate possible associations with mechanisms of resistance or sensitivity to study treatment, dynamic changes associated with study treatment (in terms of dose, safety, tolerability and efficacy, etc.) and method development or validation of diagnostic assays related to ASP0739.

The samples may be stored at the study sponsor's facility or a contract laboratory facility for up to 15 years after study database closure, at which time the samples will be destroyed. The procedures for the collection, handling and shipping of laboratory samples will be specified in a laboratory manual.

Refer to the laboratory manual for detailed information regarding sampling, processing, shipping and storage instructions.

7.5.1 Blood Samples

Blood samples will be used for the analysis of pharmacodynamics changes related to treatment effect and potential biomarkers of response or resistance related to treatment effect

as described in [Section 9.4.5.1 Analysis of Exploratory Biomarker(s)]. Examples of these biomarkers include, but are not limited to, anti-NY-ESO-1 antibodies, cytokine expression and secretion (e.g., IFNg), NY-ESO-1-specific T lymphocytes (e.g., cytotoxic T lymphocytes), immune cell populations (e.g., NKT cells, NK cells, etc.), expression levels of NY-ESO-1 and mutations in genes that may modify treatment effect.

7.5.2 Tumor Tissue Samples

The tumor tissue will be used for biomarker analyses as described in [Section 9.4.5.1 Analysis of Exploratory Biomarkers(s)]. Examples of biomarkers include, but are not limited to, expression of NY-ESO-1, expression and mutation of genes that may modify treatment effect, tumor mutational burden, changes in the tumor microenvironment and changes in immune related molecules. Examples include, but are not limited to, CD4 T-cells, CD8 T-cells, etc.

Archival tumor tissue sample: All participants are required to submit (if available) an archival tumor tissue sample in the form of a formalin-fixed, paraffin-embedded (FFPE) block or unstained slides will be collected. If unstained slides are submitted, a minimum of 20 slides (5 microns thick) is necessary.

Baseline tumor tissue sample: Participants in all expansion cohorts are required to consent to provide a tumor tissue sample (both an FFPE block and frozen sample) obtained within 56 days prior to first dose of study treatment. If the participant has both an FFPE block AND frozen tissue specimen taken within 56 days prior to the first dose of study treatment, a new biopsy is not required.

On-treatment tumor tissue sample: Participants in all expansion cohorts are required to consent to provide an on-treatment tumor tissue sample (both an FFPE block and frozen sample). On-treatment tumor tissue sample is to be collected \pm 7 days of the C2D15 visit (or unscheduled).

Details on sample collection, labeling, and shipment procedures will be provided in a separate laboratory manual.

7.5.3 Buccal Swab Samples

Buccal swab samples will be used to genotype the human leukocyte antigen (HLA) gene complex. Knowledge of the specific HLA gene complex in each participant may help understand/explain observed differences in efficacy or treatment effect. The buccal swab will be used for biomarker analyses as described in [Section 9.4.5.1 Analysis of Exploratory Biomarker(s)].

7.6 Pharmacogenomics

Pharmacogenomic (PGx) research may be conducted in the future to analyze or determine genes of relevance to clinical response, pharmacokinetics, toxicity/safety, efficacy and/or disease. A 4 to 6 mL sample of whole blood for possible banked PGx analysis will be collected as indicated in the schedules of assessments [Table 1 and Table 2] Samples will be shipped to a sponsor-designated sample banking contract research organization (CRO).

Details on sample collection, labeling, storage and shipment procedures will be provided in a separate laboratory manual.

See [Section 10.7 Appendix 7: Pharmacogenomic Analysis with Banked Sample] for further details on the banking procedures.

7.7 Other Assessments

7.7.1 Replication Competent Lentivirus

Blood samples will be collected and used to monitor the presence of replication competent lentivirus. Sampling time points are as shown in the schedule of assessments [Table 4]. If there is a positive result during the first 18 months of assessments, additional follow-up assessments may be required.

7.8 Total Amount of Blood

The total amount of blood for each participant will vary depending on the course of their disease, duration of treatment and local laboratory requirements. At any time during the study, if any laboratory abnormalities are found for a participant, additional blood may be drawn for safety monitoring.

The maximum amount of blood collected within 24 hours will be from participants on C1D1 and will not exceed 80 mL; the maximum amount of blood collected in one cycle will be during C1 and will not exceed 130 mL.

8 PARTICIPANT DISCONTINUATION

Refer to [Section 10.1.9 Study and Site Start and Closure] regarding discontinuation of study sites or of the study as a whole.

8.1 Discontinuation of Individual Participant(s) from Study Treatment

A discontinuation from treatment is defined as a participant who enrolled in the study and for whom study treatment is permanently discontinued for any reason.

The participant is free to withdraw from the study treatment and/or study for any reason and at any time without giving reason for doing so and without penalty or prejudice. The investigator is also free to discontinue the participant from study treatment or to terminate a participant's involvement in the study at any time if the participant's clinical condition warrants it.

The reason for discontinuation from study treatment must be documented in the participant's medical records.

A participant must discontinue study treatment for any of the following reasons:

- Participant requests to stop treatment.
- Any clinical AE, laboratory abnormality or intercurrent illness that, in the opinion of the investigator, indicates continued treatment is not in the best interest of the participant.

- In the combination therapy arm only, treatment will be permanently discontinued following occurrence of grade 3 to 4 myocarditis.
- Participant is found to have significantly deviated from any one of the inclusion or exclusion criteria after enrollment (participants having clinical benefit and no DLT may be kept in the study after discussion with the medical monitor).
- Participant not achieving response (CR or PR) and/or the participant is no longer deriving clinical benefit, in the opinion of the investigator.
- Participant begins other anti-cancer therapies.
- Participant experiences disease relapse/progression.
- Investigator/subinvestigator determines that the continuation of the study treatment will be detrimental to the participant.
- Participant is in need of receiving prohibited concomitant treatment(s) based on Investigator's clinical opinion.
- Participant is lost to follow-up despite reasonable efforts by the investigator to locate the participant.
- Female participant becomes pregnant.
- Death.

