Phase 1 (dose escalation) in participants with solid tumors known to express NY-ESO-1 and phase 2 of ASP0739 single agent and combination therapy with pembrolizumab in R/R SS, MRCL and ovarian cancer who have not responded to SOC or are ineligible for standard therapy.

Phase 2 single agent will also include a cohort of participants with select solid tumors known to express NY-ESO-1 (melanoma, NSCLC-adenocarcinoma and squamous cell and ESCC).

Both study phases consist of the following periods:

- Screening (up to 28 days)
- Treatment with ASP0739 (up to 6 doses every 28-days) and for participants in combination cohorts with pembrolizumab on cycle 1 day 1 (C1D1), and then every 6 weeks, until disease progression, unacceptable toxicity or up to 17 doses
- EOT visit after completion of investigational product (IP): Within 7 days of EOT determination or prior to the initiation of new anticancer therapy, whichever occurs first
- Safety follow-up visits at 30, 60 and 90 days from the last dose of treatment or prior to the initiation of new anticancer therapy
- Follow-up visits every 2 months for up to 1 year or until progression or start of a new anticancer therapy or death (whichever occurs first)
- Survival follow-up for up to 1 year by telephone calls every 3 months after the start of a new anticancer treatment or progression after ASP0739 and/or pembrolizumab treatment

ASP0739 Single Agent

Participants will receive an intravenous infusion of ASP0739 (human embryonic kidney cells [HEK293] transfected with a lentiviral vector that is encoding the target antigen NY-ESO-1).

Participants will receive 1 dose every 28-day cycle for up to 4 doses; an additional 2 doses may be administered in participants with PR or stable disease (SD). Following the first 2 cycles, participants who have not met any individual treatment discontinuation criteria and are receiving clinical benefit may continue further treatment with ASP0739, as decided by the investigator.

The starting dose is 1×10^7 cells/dose and the decision to dose escalate to the next dose level (1×10^8 cells/dose) or to dose reduce (1×10^6 cells/dose) to a lower dose level will be made based on the assessment of safety variables, including the occurrence of dose-limiting toxicities (DLTs).

Dose Levels (Phase 1 dose escalation)

Dose Level	Dose
0	1×10^7 cells/dose
+1	1×10^8 cells/dose

ASP0739 Combination with Pembrolizumab

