Archival Tumor Tissue ^q		X																					
Pulmonary function test ^z	X													X								X	
Radiographic Disease Assessment ^t	X													Every 56 ± 7 days									
IRT Transaction	X	X ^s						X						X				X				X	
ASP0739 Dosing ^t		X						X						X				X					
Pembrolizumab Dosing ^u		X											X		Every 6 weeks ^u						X		

Footnotes appear on next page

AE: adverse event; C: cycle; CR: complete response; CT: computed tomography; D: day; ECG: electrocardiogram; ECHO: echocardiogram; ECOG: eastern cooperative oncology group; ELISpot: enzyme-linked immunospot; EOT: end of treatment; FFPE: formalin-fixed, paraffin-embedded; HLA: human leukocyte antigen; ICF: informed consent form; IP: investigational product; IRT: interactive response technology; MRI: magnetic resonance imaging; MUGA: multiple gated acquisition scan; NY-ESO-1: New York esophageal squamous cell carcinoma 1; Pembro: pembrolizumab; PGx: pharmacogenomic; PR: partial response; PT/INR: prothrombin time/international normalized ratio; SAE: serious adverse event; Scr: screening; SD: stable disease; WOCBP: woman of childbearing potential

- a. Cycles 1 through 6 represent ASP0739 single agent or combination of ASP0739 and pembrolizumab therapy; each cycle is 28 days.
- b. After the first 2 cycles, participants who have not met any individual treatment discontinuation criteria and are receiving clinical benefit (defined as radiological response or SD, or reduction of disease-related symptoms) will continue further treatment of ASP0739 in cycles 3 and 4, as decided by the investigator.
- c. After the first 4 cycles, participants who achieve PR or SD may receive 2 doses of ASP0739 in cycles 5 and 6. Participants who reach CR will not receive additional doses of ASP0739.
- d. Participants in combination therapy only will continue to receive pembrolizumab as monotherapy for doses 5 up to 17. If participant receives at least 1 dose of ASP0739 but discontinues combination treatment of ASP0739 at any time prior to C5D15, then the participant may continue pembrolizumab as monotherapy for up to 96 weeks for a total of 17 doses of pembrolizumab total for the study.
- e. The EOT visit will occur within 7 days of the principal investigator decision to discontinue the participant for treatment or prior to the start of new anticancer treatment, whichever occurs first. If a participant is completing all visits in the last treatment cycle, the EOT visit will be within 7 days from the last planned visit.

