4 STUDY DESIGN AND DOSE RATIONALE

4.1 Overall Study Design

This is a phase 1, open-label study of ASP0739 in participants with R/R solid tumors known to express NY-ESO-1 and a phase 2 study of single agent and combination therapy with pembrolizumab in participants with R/R SS, MRCL or ovarian cancer.

Phase 1 (dose escalation) in participants with solid tumors known to express NY-ESO-1 and phase 2 of ASP0739 single agent and combination therapy with pembrolizumab in R/R SS, MRCL and ovarian cancer who have not responded to SOC or are ineligible for standard therapy. Phase 2 single agent will also include a cohort of participants with select solid

tumors known to express NY-ESO-1 (melanoma, NSCLC-adenocarcinoma and squamous cell and ESCC).

Both study phases consist of the following periods:

- Screening (up to 28 days)
- Treatment with ASP0739 (up to 6 doses every 28 days) and for participants in combination cohorts with pembrolizumab on cycle 1 day 1 (C1D1), and then every 6 weeks, until disease progression, unacceptable toxicity or up to 17 doses
- EOT visit after completion of IP: Within 7 days of EOT determination or prior to the initiation of new anticancer therapy, whichever occurs first
- Safety follow-up visits at 30, 60 and 90 days from the last dose of treatment or prior to the initiation of new anticancer therapy
- Follow-up visits every 2 months for up to 1 year or until progression or start of a new anticancer therapy or death (whichever occurs first)
- Survival follow-up for up to 1 year by telephone calls every 3 months after the start of a new anticancer treatment or progression after ASP0739 and/or pembrolizumab treatment

ASP0739 Single Agent

Participants will receive an intravenous infusion of ASP0739 (HEK293 transfected with a lentiviral vector that is encoding the target antigen NY-ESO-1). Participants will receive 1 dose every 28-day cycle for up to 4 doses; an additional 2 doses may be administered in participants with a partial response (PR) or stable disease (SD). Following the first 2 cycles, participants who have not met any individual treatment discontinuation criteria and are receiving clinical benefit may continue further treatment with ASP0739, as decided by the investigator.

ASP0739 Combination with Pembrolizumab

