The recommended phase 2 dose (RP2D) of ASP0739 determined from the phase 1 dose escalation phase will be combined with pembrolizumab 400 mg for the safety lead-in with approximately 6 to 9 participants. If the RP2D is selected at the same dose level as the maximum tolerated dose (MTD) based on the phase 1 dose escalation portion, the combination safety lead-in will start at one dose level lower than the MTD.

If DLTs occur in the safety lead-in cohort and the dose level is de-escalated to a lower dose level per BOPIN design (either from 1×10^8 to 1×10^7 or from 1×10^7 to 1×10^6), the dose de-escalation cohort enrollment must be completed and determined to be safe by the DESC before enrollment in the ASP0739 and pembrolizumab combination expansion cohorts.

Participants will receive 1 dose of ASP0739 every 28-day cycle for a total of 4 doses; an additional 2 doses may be administered for participants with PR or SD. Following the first 2 cycles, participants who have not met any individual treatment discontinuation criteria and are receiving clinical benefit may continue further treatment with ASP0739 and pembrolizumab, as decided by the investigator. Participants will also receive pembrolizumab 400 mg on C1D1, then every 6 weeks, until disease progression, unacceptable toxicity or for up to 17 doses or until one of the discontinuation criteria is met. For combination treatment, a

400 mg pembrolizumab infusion will be administered first, followed by an ASP0739 infusion at least 1 hour after the completion of the pembrolizumab infusion.

Phase 1 Single Agent Dose Escalation:

The single agent dose escalation phase will evaluate escalating dose levels of ASP0739 in approximately 3 to 12 DLT-evaluable participants.

The starting dose is 1×10^7 cells/dose and the decision to dose escalate to the next dose level (1×10^8 cells/dose) or to dose reduce (1×10^6 cells/dose) to a lower dose level will be made based on the assessment of safety variables, including the occurrence of dose-limiting toxicities (DLTs).

Table 8 Dose Levels (Phase 1 Dose Escalation)

Dose Level	Dose
0	1×10^7 cells/dose
+1	1×10^8 cells/dose

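### Read literally, Protocol Section 8.1 makes failure to reach CR or PR a mandatory reason to stop treatment, contradicting the dosing rules that continue ASP0739 in stable disease

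*Protocol*

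**What the plan says.** Protocol Section 8.1 introduces its list with "A participant must discontinue study treatment for any of the following reasons". One entry reads "Participant not achieving response (CR or PR) and/or the participant is no longer deriving clinical benefit, in the opinion of the investigator". A separate entry covers progression: "Participant experiences disease relapse/progression".

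The dosing rules treat SD as a reason to go on:

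- **After cycle 2.** Section 4.1 says that "participants who have not met any individual treatment discontinuation criteria and are receiving clinical benefit may continue further treatment with ASP0739". Footnote b of Tables 1 and 2, repeated in Tables 18 and 19, applies this to participants who "are receiving clinical benefit (defined as radiological response or SD, or reduction of disease-related symptoms"), subject to the investigator's decision.
- **After cycle 4.** For combination therapy, Section 4.1 says "an additional 2 doses may be administered for participants with PR or SD". The single-agent text, the synopsis and footnote c of the same four tables say the same in substance. Footnote c gives no further ASP0739 to participants who reach CR.

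**The concern.** The stem of the list is mandatory and each entry is sufficient by itself. In the disputed entry, 'and/or' lets lack of CR or PR stand alone as a trigger. That catches participants with SD, whom the dosing schedule expects to keep treating.

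At stake is who stays on treatment and how many doses they receive. A site that follows Section 8.1 to the letter would take participants with SD off a regimen that Section 4.1 gives them. A site that follows Section 4.1 would leave in place participants who meet a listed stopping reason. There is a possible consequence for reporting: SAP Section 6.2.2 counts, as deviation PD2, participants who met withdrawal criteria and were not withdrawn. If PD2 is judged against Section 8.1, a participant with SD who was dosed correctly under Section 4.1 could be counted. Nothing in the documents shows that this happened.

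No effect on response rate, power or analysis sets is claimed.

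**Working it through.** The plan states no figure on this point, so the check is a comparison of texts followed by a bound on the doses affected.

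**Logic.** Let A be that the participant has not achieved CR or PR, and B that the participant is no longer deriving clinical benefit. Take a participant with SD. A is true. B is false, because footnote b counts SD as clinical benefit.

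- Under 'A or B', the criterion is met and Section 8.1 requires stopping.
- Under 'A and B', the criterion is not met and there is no conflict.
- 'And/or' includes the 'or' case, so the literal text requires stopping.

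**Does another rule resolve it?**

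- Continuation after cycle 2 is open only to participants who have met no discontinuation criterion. On the literal reading, the participant with SD has met one, so Section 8.1 overrides the continuation rule.
- For cycles 5 and 6, CR is excluded by footnote c. If SD were excluded by Section 8.1, only PR would remain and the mention of SD would have no effect.
- Progression has its own entry in Section 8.1. Limb A therefore adds only non-responders who have not progressed, chiefly participants with SD.
- Limb A carries no time point. Before the first post-baseline scan nobody has a documented CR or PR, so read literally it is true of every participant from the first dose.

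**Doses affected.** Assumptions: the rule is applied on the date of the first scan, and dosing is on schedule. Inputs are the scan interval and visit windows in Tables 1 and 2, counted as days after C1D1.

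- First scan: 56 ± 7, days 49 to 63.
- Dose 2: 28 ± 1, days 27 to 29.
- Dose 3: 56 ± 3, days 53 to 59.
- Dose 4: 84 ± 3, days 81 to 87.

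Dose 2 always precedes the scan (29 < 49). Dose 3 may fall on either side of it, because the ranges overlap. Dose 4 always follows it (81 > 63). The participant has therefore had 2 or 3 doses by the first scan, never 4.

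- Against 4 doses: 4 − 3 = 1 fewer (25%) to 4 − 2 = 2 fewer (50%).
- Against the maximum of 6: 6 − 3 = 3 fewer (50%) to 6 − 2 = 4 fewer (67%).

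These are ceilings, because doses 3 and 4 are at the investigator's decision and doses 5 and 6 are optional. On the benefit-based reading the loss is 0.

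**The case against.** The strongest reply is that nobody would apply the bullet this way. It ends by deferring to the investigator's opinion, and that qualifier can be read as governing the whole entry, which makes it a judgement rather than an automatic trigger. The eight places that continue treatment in SD (two in the synopsis, two in Section 4.1 and four sets of table footnotes) are two rules repeated consistently, so a site is unlikely to be led astray by one loose phrase. The dose figures quantify only the less likely reading. They also assume a decision at week 8, when SD can still become a response and a response still needs a confirmatory scan at least 4 weeks later.

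Much of this stands. The benefit-based reading is the probable intent, and the dose figures are bounds under a stated assumption rather than expected losses. What does not stand is that the qualifier removes the conflict. Even if it governs both limbs, an investigator who judges that there is no CR or PR has still met a listed reason, and the stem then requires stopping. The consistency of the dosing rules shows what was meant, but the protocol gives no order of precedence, and the continuation rule after cycle 2 itself defers to the discontinuation criteria.

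**Conclusion.** The point holds, at minor severity. As written, Section 8.1 contains a mandatory stopping criterion that covers participants with SD and contradicts the protocol's own dosing rules.

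If the criterion were applied at the first scan, the ceiling is 1 to 4 doses lost for a participant who would otherwise have reached between four and six. It is zero on the likely intent.

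The practical effect is limited in two further ways. Imaging continues every 8 weeks regardless of treatment interruption (Section 7.1) and participants who stop treatment stay in follow-up (Section 8.2), so outcome assessment is not cut short. SAP Section 1 records that the study ended early.

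**What to change.** Replace the bullet in Section 8.1 with a single criterion based on benefit, for example: *In the investigator's opinion, the participant no longer has clinical benefit (radiological response, SD or symptom reduction, as in footnote b of the Schedules of Assessments).* Leave the progression entry unchanged. Deleting the CR/PR limb and keeping the rest would also remove the conflict; the fuller wording has the advantage of tying the criterion to the protocol's own definition. Neither version names a scan. A criterion based on loss of benefit does not depend on one in the way that failure to respond does, although before the first scan it still rests on the investigator's judgement.

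The cost is the wording of one bullet, with no change to data collection, sample size or analyses.

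A separate clerical point: SAP Section 6.2.2 cites a protocol Section 8.1.6 that is not in the protocol supplied (Amendment 4). It may refer to another version. The cross-reference should be corrected.
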